### 2. INTRODUCTION

The BNT162 RNA-based COVID-19 vaccines are currently being investigated for prevention of COVID-19 in healthy adults.

# 2.1. Study Rationale

The purpose of the study is to rapidly describe the safety, tolerability, and immunogenicity of BNT162 RNA-based COVID-19 vaccine candidate against COVID-19 in healthy Japanese adults. There are currently no licensed vaccines to prevent infection with SARS-CoV-2 or COVID-19. Given the global crisis of COVID-19 and fast expansion of the disease globally, including Japan, the rapid development of an effective vaccine is of utmost importance.

# 2.2. Background

In December 2019, a pneumonia outbreak of unknown cause occurred in Wuhan, China. In January 2020, it became clear that a 2019-nCoV was the underlying cause. Later in January, the genetic sequence of the 2019-nCoV became available to the World Health Organization (WHO) and public (MN908947.3), and the virus was categorized in the *Betacoronavirus* subfamily. By sequence analysis, the phylogenetic tree revealed a closer relationship to severe acute respiratory syndrome (SARS) virus isolates than to another coronavirus infecting humans, the Middle East respiratory syndrome (MERS) virus.

The outbreak was declared a Public Health Emergency of International Concern on 30 January 2020. On 12 February 2020, the virus was officially named as SARS-CoV-2, and the WHO officially named the disease caused by SARS-CoV-2 as coronavirus disease 2019 (COVID-19).

SARS-CoV-2 infections and the resulting disease, COVID-19, have spread globally, affecting a growing number of countries.

On 11 March 2020, the WHO characterized the COVID-19 outbreak as a pandemic. The WHO Situation Update Report dated 30 March 2020 noted 693,224 confirmed cases with 33,106 deaths globally, including 142,081 confirmed cases with 2457 deaths in the Americas. The number of confirmed cases continues to rise globally. There are currently no licensed vaccines to prevent infection with SARS-CoV-2 or COVID-19.

A prophylactic, RNA-based SARS-CoV-2 vaccine provides one of the most flexible and fastest approaches available to immunize against the emerging virus.  BioNTech has developed RNA-based vaccine candidates using a platform approach that enables the rapid development of vaccines against emerging viral diseases, including SARS CoV-2.

The development of an RNA-based vaccine encoding a viral antigen, which is then expressed by the vaccine recipient as a protein capable of eliciting protective immune responses, provides significant advantages over more traditional vaccine approaches. Unlike live attenuated vaccines, RNA vaccines do not carry the risks associated with infection and may be given to people who cannot be administered live virus (eg, pregnant women and immunocompromised persons). RNA-based vaccines are manufactured via a cell-free

in vitro transcription process, which allows an easy and rapid production and the prospect of producing high numbers of vaccination doses within a shorter time period than achieved with traditional vaccine approaches. This capability is pivotal to enable the most effective response in outbreak scenarios.

Two SARS-CoV-2–RNA lipid nanoparticle (RNA-LNP) vaccines based on a platform of nucleoside-modified messenger RNA (modRNA, BNT162b) will be evaluated in a Phase 1/2/3 study (C4591001) conducted in the United States. Each vaccine candidate expresses 1 of 2 antigens: the SARS-CoV-2 full-length, P2 mutant, prefusion spike glycoprotein (P2 S) (version 9) (BNT162b2 [variant RBP020.2]: a modRNA encoding P2 S) or a trimerized SARS-CoV-2 spike glycoprotein-receptor binding domain (RBD) (version 5) (BNT162b1 [variant RBP020.3]: a modRNA encoding the RBD). The vaccine candidate selected for Phase 2/3 evaluation in the C4591001 study is BNT162b2.

This study will evaluate the safety, tolerability, and immunogenicity of a vaccine candidate (BNT162b2) in Japanese adults 20 to 85 years of age.

### 2.2.1. Clinical Overview

Prior to this study, given clinical data from other similarly formulated uRNA liposomal vaccines from BioNTech in oncology trials and recent published results from clinical trials using modRNA influenza vaccines by Moderna, the BNT162 vaccines were expected to have a favorable safety profile with mild, localized, and transient effects. BNT162 vaccines based on modRNA have now been administered to humans for the first time in the C4591001 study and the BNT162-01 study conducted in Germany by BioNTech, at doses between 1 µg and 100 µg. The currently available safety and immunogenicity data are presented in the BNT162 IB.

# 2.3. Benefit/Risk Assessment

There is an ongoing global pandemic of COVID-19 with no preventive or therapeutic options available. There are accumulating data from ongoing human clinical trials of BNT162 vaccines in the United States and Germany, with an acceptable safety and tolerability profile observed at the time of initiation of this study. In addition, available nonclinical data with these vaccines, and data from nonclinical studies and clinical trials with the same or related RNA components, or antigens, supported a favorable risk/benefit profile. Anticipated AEs after vaccination were expected to be manageable using routine symptom-driven standard of care as determined by the investigators and, as a result, the profile of these vaccine candidates supported initiation of this Phase 1/2 clinical study.

More detailed information about the known and expected benefits and risks and reasonably expected AEs of BNT162 RNA-based COVID-19 vaccines may be found in the IB, which is the SRSD for this study.

# 2.3.1. Risk Assessment

Potential Risk of Clinical Significance	Summary of Data/Rationale for Risk	Mitigation Strategy
	Study Intervention: BNT162 RNA-Ba	sed COVID-19 Vaccine
Potential for local reactions (injection site redness, injection site swelling, and injection site pain) and systemic events (fever, fatigue, headache, chills, vomiting, diarrhea, muscle pain, and joint pain) following vaccination.	These are common adverse reactions seen with other vaccines, as noted in the FDA CBER guidelines on toxicity grading scales for healthy adult volunteers enrolled in preventive vaccine clinical trials.8	The study employs the use of a reactogenicity e-diary to monitor local reactions and systemic events in real time. Study clinicians will closely monitor for severe reactions. In addition, investigators will contact participants and conduct unscheduled visits for any reported severe local reactions or systemic events.
Unknown AEs and laboratory abnormalities with a novel vaccine.	Accumulating safety data from ongoing clinical studies have shown an acceptable safety profile. Known laboratory abnormalities from the clinical studies conducted in the United States and Germany include transient and self-limited reduction in lymphocyte counts.	The study design includes the use of a clinical laboratory subset to monitor participants for laboratory abnormalities. Participants will be observed for 30 minutes after vaccination to assess for immediate AEs.
Potential for COVID-19 disease enhancement.	Disease enhancement has been seen following vaccination with respiratory syncytial virus (RSV), feline coronavirus, and Dengue virus vaccines.	Participants with likely previous or current COVID-19 will be excluded. All participants will be followed for SARS-CoV-2 antigen-specific antibody and SARS-CoV-2 serum neutralizing titers, and COVID-19 illness, including markers of severity.
	Study Procedur	es
Participants will be required to attend healthcare facilities during the global SARS-CoV-2 pandemic.	Without appropriate social distancing and PPE, there is a potential for increased exposure to SARS-CoV-2.	Pfizer will work with sites to ensure an appropriate COVID-19 prevention strategy. Potential COVID-19 illness visits can be conducted via telehealth, without the need for an in-person visit, if required, with the participant performing a self-swab.
Venipuncture will be performed during the study.	There is the risk of bleeding, bruising, hematoma formation, and infection at the venipuncture site.	Only appropriately qualified personnel will obtain the blood draw.

# 2.3.2. Benefit Assessment

Benefits to individual participants may include:

- Receipt of a potentially efficacious COVID-19 vaccine during a global pandemic
- Access to COVID-19 diagnostic and antibody testing
- Contributing to research to help others in a time of global pandemic

# 2.3.3. Overall Benefit/Risk Conclusion

Taking into account the measures taken to minimize risk to participants participating in this study, the potential risks identified in association with BNT162 RNA-based COVID-19 vaccine are justified by the anticipated benefits that may be afforded to healthy participants.

# 3. OBJECTIVES, ESTIMANDS, AND ENDPOINTS

Objectives	Estimands	Endpoints
	Primary Safety:	
To describe the safety and tolerability profiles of a prophylactic BNT162 vaccine in healthy Japanese adults after 2 doses	
 
In participants receiving at least 1 dose of study intervention, the percentage of participants reporting:
 
Local reactions for up to 7 days following each dose
 
Systemic events for up to 7 days following each dose
 
AEs from Dose 1 to 1 month after Dose 2
 
SAEs from Dose 1 to 12 months after Dose 2
 
In addition, in a clinical laboratory subset, the percentage of participants with:
 
Abnormal hematology and chemistry laboratory values 1 and 7 days after Dose 2
 
Grading shifts in hematology and
 
	
 
Local reactions (pain at the injection site, redness, and swelling)
 
Systemic events (fever, fatigue, headache, chills, vomiting, diarrhea, new or worsened muscle pain, and new or worsened joint pain)
 
AEs
 
SAEs
 
Hematology and chemistry laboratory parameters detailed in Section 10.2
 

	chemistry laboratory assessments between baseline and 1 and 7 days after Dose 1; and before Dose 2 and 7 days after Dose 2	

Objectives	Estimands	Endpoints
	Primary Immunogenicity:	
To describe the immune responses elicited by a prophylactic BNT162 vaccine in healthy Japanese adults	In participants complying with the key protocol criteria (evaluable participants):  • GMTs 1 month after Dose 2  • GMFR from before vaccination to 1 month after Dose 2	SARS-CoV-2 serum neutralizing titers
	Secondary Immunogenicity:	
To describe the immune responses elicited by a prophylactic BNT162 vaccine in healthy Japanese adults	In the evaluable participants, at baseline, 21 days after Dose 1; 7 and 14 days and 6 and 12 months after Dose 2:  GMTs at each time point GMFR from before vaccination to each subsequent time point after vaccination	SARS-CoV-2 serum neutralizing titers
To describe the immune responses elicited by a prophylactic BNT162 vaccine in participants with/without confirmed COVID-19 before Dose 2	
 
In the evaluable participants, at baseline, 21 days after Dose 1; 7 and 14 days and 1, 6, and 12 months after Dose 2:
 
GMTs at each time point
 
GMFR from before vaccination to each subsequent time point after vaccination
 
	SARS-CoV-2 serum neutralizing titers
	Exploratory Immunogenicity	:
To describe the immune responses elicited by prophylactic BNT162 vaccine in participants with/without confirmed COVID-19 during the study	In the evaluable participants, at baseline, 21 days after Dose 1; 7 and 14 days and 1, 6, and 12 months after Dose 2:  GMTs at each time point GMFR from before vaccination to each subsequent time point after vaccination	SARS-CoV-2 serum neutralizing titers
To evaluate the immune response (non-S) to SARS-CoV-2 in participants with/without confirmed COVID-19 during the study		SARS-CoV-2 N-binding antibody

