#### 8. STUDY ASSESSMENTS AND PROCEDURES

The investigator (or an appropriate delegate at the investigator site) must obtain a signed and dated ICD before performing any study-specific procedures.

The full date of birth will be collected to critically evaluate the immune response and safety profile by age.

Study procedures and their timing are summarized in the SoA. Protocol waivers or exemptions are not allowed.

Safety issues should be discussed with the sponsor immediately upon occurrence or awareness to determine whether the participant should continue or discontinue study intervention.

Adherence to the study design requirements, including those specified in the SoA, is essential and required for study conduct.

All screening evaluations must be completed and reviewed to confirm that potential participants meet all eligibility criteria. The investigator will maintain a screening log to record details of all participants screened and to confirm eligibility or record reasons for screening failure, as applicable.

Every effort should be made to ensure that protocol-required tests and procedures are completed as described. However, it is anticipated that from time to time there may be circumstances outside the control of the investigator that may make it unfeasible to perform the test. In these cases, the investigator must take all steps necessary to ensure the safety and well-being of the participant. When a protocol-required test cannot be performed, the investigator will document the reason for the missed test and any corrective and preventive actions that he or she has taken to ensure that required processes are adhered to as soon as possible. The study team must be informed of these incidents in a timely manner.

For samples being collected and shipped, detailed collection, processing, storage, and shipment instructions and contact information will be provided to the investigator site prior to initiation of the study.

The total blood sampling volume for individual participants in this study is approximately 225 mL for the clinical laboratory subset and 175 mL for the standard participants. Other additional blood samples may be taken for safety assessments at times specified by Pfizer,

provided the total volume taken during the study does not exceed 550 mL during any period of 60 consecutive days.

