#### 8.11.1.5. Visit 4 – Vaccination 2 (19 to 23 Days After Visit 1)

It is anticipated that the procedures below will be conducted in a stepwise manner; ensure that procedures listed prior to administration of the vaccine are conducted prior to vaccination.

• Record AEs as described in Section 8.3.

- Review the participant's reactogenicity e-diary data. Collect stop dates of any reactogenicity e-diary events ongoing on the last day that the reactogenicity e-diary was completed and record stop dates in the CRF if required.
- Review hematology and chemistry laboratory results and record any AEs in accordance with Appendix 2.
- Perform a clinical assessment. If the clinical assessment indicates that a physical examination is necessary to comprehensively evaluate the participant, perform a physical examination and record any findings in the source documents and, if clinically significant, record on the AE CRF.
- Perform urine pregnancy test on WOCBP as described in Section 8.2.4.
- Discuss contraceptive use as described in Section 10.4.
- Collect a blood sample (approximately 10 mL) for hematology and chemistry laboratory tests as described in Section 10.2.
- Record nonstudy vaccinations as described in Section 6.5.
- Confirm details of any of the prohibited medications specified in Section 6.5.1 received by the participant if required for his or her clinical care.
- Ensure and document that all of the inclusion criteria and none of the exclusion criteria are met. Participants who have a positive SARS-CoV-2 NAAT result prior to the Vaccination 2 visit should be handled as described in Section 8.15.
- Measure the participant's body temperature (axillary).
- Ensure that the participant meets none of the temporary delay criteria as described in Section 5.5.
- Collect a blood sample (approximately 25 mL) for immunogenicity testing.
- Obtain a nasal (midturbinate) swab (collected by site staff).
- Unblinded site staff member(s) will dispense/administer 1 dose of study intervention into the deltoid muscle of the preferably nondominant arm. Please refer to the IP manual for further instruction on this process.
- Blinded site staff must observe the participant for at least 30 minutes after study intervention administration for any acute reactions. Record any acute reactions (including time of onset) in the participant's source documents and on the AE page of the CRF, and on an SAE form as applicable.

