### 9.4.2. Safety Analyses

Endpoint	Statistical Analysis Methods
Primary	Descriptive statistics will be provided for each reactogenicity endpoint for each vaccine group. Local reactions and systemic events from Day 1 through Day 7 after each vaccination will be presented by severity cumulatively across severity levels. Descriptive summary statistics will include counts and percentages of participants with the indicated endpoint and the associated Clopper-Pearson 95% CIs.
	For the clinical laboratory subset, descriptive statistics will be provided for abnormal hematology and chemistry laboratory values at 1 and 7 days after Dose 1 and 7 days after Dose 2, including grading shifts in hematology and chemistry laboratory assessments between baseline and 1 and 7 days after Dose 1, and before Dose 2 and 7 days after Dose 2. Descriptive summary statistics will include counts and percentages of participants with the indicated endpoint and the associated Clopper-Pearson 2-sided 95% CIs.
	AEs will be categorized according to Medical Dictionary for Regulatory Activities (MedDRA) terms. A 3-tier approach will be used to summarize AEs. Under this approach AEs are classified into 1 of 3 tiers: (1) Tier 1 events are prespecified events of clinical importance and are identified in a list in the product's safety review plan; (2) Tier 2 events are those that are not Tier 1 but are considered "relatively common"; a MedDRA preferred term is defined as a Tier 2 event if there are at least 4 of participants in at least 1 vaccine group reporting the event; and (3) Tier 3 events are those that are neither Tier 1 nor Tier 2 events. For both Tier 1 and Tier 2 events, 2-sided 95% CIs for the difference between the vaccine and placebo groups in the percentage of participants reporting the events based on the

Endpoint	Statistical Analysis Methods
	Miettinen and Nurminen method  will be provided. In addition, for Tier 1 events, the asymptotic p-values will also be presented for the difference between groups in the percentage of participants reporting the events, based on the same test statistic and under the assumption that the test statistic is asymptotically normally distributed.
	Descriptive summary statistics (counts, percentages, and associated Clopper-Pearson 95% CIs) will be provided for any AE events for each vaccine group.

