#### 2.1. Study Objectives, Endpoints, and Estimands

The estimands corresponding to each primary, secondary, and exploratory objective are described in Table 2 below.

In the primary safety objective evaluations, missing e-diary data will not be imputed. Missing AE dates will be imputed according to Pfizer safety rules. No other missing information will be imputed in the safety analysis.

The estimands to evaluate the immunogenicity objectives are based on evaluable populations for immunogenicity (see Section 4 for definition). These estimands estimate vaccine effect in the hypothetical setting where participants follow the study schedules and protocol requirements as directed. Missing antibody results will not be imputed. Immunogenicity results that are below the LLOQ will be set to  $0.5 \times LLOQ$  in the analysis; this may be adjusted once additional data on the assay characteristics become available.

Objectives	Estimands	Endpoints
Primary Safety:	•	
To describe the safety and tolerability profiles of a prophylactic BNT162 vaccine in healthy Japanese adults after 2 doses	
 
In participants receiving at least 1 dose of study intervention, the percentage of participants reporting:
 
Local reactions for up to 7 days following each dose
 
Systemic events for up to 7 days following each dose
 
AEs from Dose 1 to 1 month after Dose 2
 
SAEs from Dose 1 to 12 months after Dose 2
 
	
 
Local reactions (pain at the injection site, redness, and swelling)
 
Systemic events (fever, fatigue, headache, chills, vomiting, diarrhea, new or worsened muscle pain, and new or worsened joint pain)
 
AEs
 
SAEs
 

	
 
In addition, in a clinical laboratory subset, the percentage of participants with:
 
Abnormal hematology and chemistry laboratory values 1 and 7 days after Dose 1; and 7 days after Dose 2
 
Grading shifts in hematology and chemistry laboratory assessments between baseline and 1 and 7 days after Dose 1; and before Dose 2 and 7 days after Dose 2
 
	• Hematology and chemistry laboratory parameters detailed in the protocol, Section 10.2.

 Table 2.
 List of Primary, Secondary, and Exploratory Objectives, Estimands, and Endpoints

Objectives	Estimands		Endpoints
Primary Immunogenicity:		1	

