#### 6.1.1.5. Hematology and Chemistry Parameters (for Clinical Laboratory Subset)

#### 6.1.1.5.1. Main Analyses

- Estimands: The percentage of participants with abnormal hematology and chemistry laboratory values 1 and 7 days after Dose 1; and 7 days after Dose 2 (Section 2.1).
- The percentage of participants with grading shifts in hematology and chemistry laboratory assessments between baseline and 1 and 7 days after Dose 1; and before Dose 2 and 7 days after Dose 2 (Section 2.1).

- Analysis set: Safety population including clinical laboratory subset only (Section 4).
- Analysis time point: 1 and 7 days after Dose 1; and 7 days after Dose 2.
- Analysis methodology: Descriptive statistics including counts and percentage (Section 5.2.1).
- Intercurrent events and missing data: Missing values will not be imputed.
- Reporting results: Descriptive summary statistics will be provided including counts and percentages of participants with the indicated endpoint and the associated Clopper-Pearson 2-sided 95% CIs for each vaccine group by age category (20 to 64 years of age and 65 to 85 years of age).

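### Does the primary laboratory analysis rest on a blood sample one day after Dose 2 that is never scheduled, and does it lose the pre-Dose 2 sample?

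*Protocol*

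**What the plan says.** The primary safety estimands for the clinical laboratory subset have two parts: the percentage of participants with abnormal values, and grading shifts.

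**Abnormal values.** The estimand table in Protocol Section 3, and the same table in Synopsis 1.1, reads "Abnormal hematology and chemistry laboratory values 1 and 7 days after Dose 2". Protocol 9.4.2 instead plans descriptive statistics for "abnormal hematology and chemistry laboratory values at 1 and 7 days after Dose 1 and 7 days after Dose 2". SAP 2.1 (Table 2) has "Abnormal hematology and chemistry laboratory values 1 and 7 days after Dose 1; and 7 days after Dose 2". SAP 3.1.1.6 gives the same time points, and SAP 6.1.1.5.1 fixes "Analysis time point: 1 and 7 days after Dose 1; and 7 days after Dose 2".

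**Grading shifts.** Protocol 9.4.2 has "between baseline and 1 and 7 days after Dose 1, and before Dose 2 and 7 days after Dose 2". SAP 6.1.1.5.1 has "between baseline and 1 and 7 days after Dose 1; and before Dose 2 and 7 days after Dose 2". The semicolon form also stands in Protocol Section 3 and the Synopsis, so 9.4.2 is the only place with a comma.

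**Sampling.** The schedule of activities (Protocol 1.3.1) places hematology and chemistry draws at Screening and Visits 2, 3, 4 and 5. Visit 4 is the Dose 2 visit, and its procedures, listed ahead of vaccination, include "Collect a blood sample (approximately 10 mL) for hematology and chemistry laboratory tests as described in Section 10.2". Protocol Section 8 adds: "The total blood sampling volume for individual participants in this study is approximately 225 mL for the clinical laboratory subset".

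**The concern.** Protocol 9.1.1 sends the reader to the Section 3 table for the definition of every estimand. Taken at its word, the abnormal-value bullet there asks for a percentage at a time when nobody is scheduled to be bled, and it drops both time points after Dose 1. If the analysis followed it, half of the named time points would be empty and the early post-Dose 1 data would go unreported. Those are the data behind the transient lymphocyte reduction that Protocol 2.3.1 mentions.

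Two further points seem to add to this. The sample before Dose 2 is drawn but is not an abnormal-value time point, so an abnormality present only then would be in no abnormal-value row. And the shift sentence has a single 'between'. It can be read as two pairs (baseline to 1 and 7 days after Dose 1; before Dose 2 to 7 days after Dose 2) or as one list of four comparisons with baseline. On the first reading, an abnormality that arises before Dose 2 and persists shows no upward shift, and no table compares the grade after Dose 2 with the baseline defined in SAP 3.4. The laboratory subset is the protocol's stated safeguard against unknown laboratory abnormalities, so a blind spot there would deserve attention.

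**Working it through.** **1. How many laboratory draws are there?** Inputs: about 10 mL per laboratory draw and about 25 mL per immunogenicity draw (Protocol 1.3.1); immunogenicity draws at Visits 1, 4, 5, 6, 7, 8 and 9, which is 7.

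- Laboratory draws at Screening and Visits 2, 3, 4, 5: 5 × 10 = 50 mL.
- Immunogenicity: 7 × 25 = 175 mL.
- Total: 50 + 175 = 225 mL, the figure in Protocol Section 8. Standard participants have only the 175 mL, which also matches.
- A further draw one day after Dose 2 would give 6 × 10 + 175 = 235 mL, which does not match.

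So the design has no draw one day after Dose 2. An unscheduled test remains possible (Protocol 8.2.1).

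**2. Which time points have a sample?**

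| Time point | Scheduled draw | Section 3 and Synopsis bullet | Protocol 9.4.2 and SAP |
|---|---|---|---|
| 1 day after Dose 1 | Visit 2 (1 to 3 days) | no | yes |
| 7 days after Dose 1 | Visit 3 (6 to 8 days) | no | yes |
| Before Dose 2 | Visit 4 | no | shift wording only |
| 1 day after Dose 2 | none | yes | no |
| 7 days after Dose 2 | Visit 5 (6 to 8 days after Visit 4) | yes | yes |

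All three abnormal-value time points in 9.4.2 and the SAP are sampled. The bullet has one sampled and one unsampled.

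**3. How did the bullet arise?** Compare it with the SAP 2.1 bullet. Delete from the SAP text the words between its two mentions of the seven-day interval, and the Section 3 bullet is left word for word. That is the usual trace of a skipped line in copying. It also explains why the Dose 1 time points vanish while a one-day value becomes attached to Dose 2.

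**4. Which reading of the shift sentence do the documents support?** The SAP 6.1.1.5.1 list of analysis time points covers both laboratory estimands and does not include the sample before Dose 2. If that sample were to be compared with baseline it would be an outcome time point and should be listed. If it is the reference for the Dose 2 shift, its absence is expected. The semicolon, used everywhere except 9.4.2, also separates the sentence into two pairs.

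**5. What does the two-pair reading leave out?** Scheduled post-Dose 1 samples: 24 × 4 = 96.

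- No abnormal-value row: Visit 4, 24/96 = 25%.
- No shift measured from baseline: Visits 4 and 5, 48/96 = 50%. The Visit 5 half of these still has an abnormal-value row and a shift from Visit 4.

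Follow two grade paths (baseline, Visits 2, 3, 4, 5), taking abnormal to mean Grade 1 or higher:

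- 0, 0, 0, 2, 2: no upward shift from Visit 4 to Visit 5, but counted as abnormal 7 days after Dose 2. Exclusion criterion 14 (Protocol 5.2) admits at most a stable Grade 1 value at screening, and none for bilirubin, so a Grade 2 value is known to be new.
- 0, 0, 0, 2, 0: in no abnormal-value row, but visible as the starting grade in the Visit 4 to Visit 5 shift. The Visit 4 result is available for the Visit 5 review (Protocol 8.11.1.6), and if clinically significant it is recorded as an AE (Protocol 8.2.1 and Appendix 2).

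**6. How often might the second path occur?** The documents give no rate. Assume 18 vaccinees in the subset (3:1 of 24) and a true rate p of an abnormality seen only at Visit 4. The chance of at least one is 1 − (1 − p)^18: 16.5% at p = 1%, 30.5% at 2%, 60.3% at 5% and 85.0% at 10%. The range follows entirely from the assumed p.

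**The case for a change.** The best argument for acting is that Section 3 is where the protocol says its estimands live, so an error there is more than cosmetic. Section 9 also requires major changes to primary endpoint definitions to appear in an amendment. In addition, no sentence expressly settles the shift wording, and the missing tables could be made from data already collected, in 24 people, with no new procedure.

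The bullet is indeed wrong. But the protocol itself states the sampled time points in 9.4.2, so the SAP is following the protocol and not modifying an endpoint. An analyst has one set of time points that can be produced, and it is the set in the governing analysis sections.

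The sentence could be tighter, but the two readings are not equally supported (step 4). On the better-supported one, taking the value just before Dose 2 as the reference isolates what follows Dose 2, which is a proper question.

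The call for baseline-referenced tables is weaker than it looks. The primary objective asks for the safety profile after two doses and names no baseline reference, and the row at 7 days after Dose 2 describes that state directly. Confusion of new with old abnormalities is confined to Grade 1 among graded non-bilirubin parameters. Parameters without a grade in SAP Table 7, such as hematocrit or MCV, cannot show a grading shift under that scale whichever reference is used.

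**Conclusion.** No change to the plan follows. The Section 3 and Synopsis bullet is a copying slip. Protocol 9.4.2 and three SAP sections carry the correct time points, every one is sampled, and the 225 mL total confirms the schedule. Correcting the bullet would alter no table and no number.

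Leaving the pre-Dose 2 sample out of the abnormal-value rows, and using it as the Dose 2 reference, is a fair choice in a descriptive analysis of 24 participants with no hypothesis test. It contradicts nothing in either document. What goes without a separate abnormal-value row is 24 of 96 post-Dose 1 samples; their grades still enter the shift table, and clinically significant findings enter the AE analysis, itself a primary endpoint.

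This conclusion rests on three things. The two-pair reading of the shift sentence is well supported but not stated outright. The grade paths assume that abnormal means Grade 1 or higher, whereas SAP 3.1.1.6 defers the primary criterion to a sponsor rule book that is not part of these documents. The 16.5% to 85.0% range depends on assumed event rates and on 3:1 allocation within the subset, so it carries no weight as evidence of harm to the analysis.
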